5.4 Allocation of Patient Numbers

All patients who signed the ICF for study TIRCON2012V1 will have been assigned a unique 6-digit number, where the first 3 digits represent the site code and the last 3 are sequentially assigned to each patient. These assigned numbers will be maintained for patients who continue on to study TIRCON2012V1-EXT.

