3.2 Determination of Sample Size and Study Power

There was no formal sample size and power calculation for this study. All patients who completed TIRCON2012V1 study were invited to enroll in the extension study. Among the 89 subjects randomized in TIRCON2012V1 study, 76 completed the study and 68 subjects were subsequently enrolled in this extension study (44 originally randomized to the deferiprone group and 24 in the placebo group).

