3.3 Analysis Populations

The following study populations will be used for analysis: Safety, Intent-to-Treat (ITT), and Per-Protocol (PP). The safety population will be used for the analysis of safety endpoints. The ITT population will represent the primary analysis population for the evaluation of efficacy endpoints, and the PP population will be the secondary efficacy analysis population.

Safety Population

The Safety population will include all patients who took at least one dose of study drug in the extension study.

ITT Population

The ITT population will include all enrolled patients who received at least one dose of study drug and have a baseline and at least one post-baseline efficacy assessment in the extension study.

PP Population

The PP population will include all enrolled patients who complete the extension study and have an efficacy assessment at the end of the study, have no major protocol violations, and have no change in DBS and baclofen pump settings or medications that could have an impact on dystonia. Prior to database lock, protocol deviations and medications that could have an impact on dystonia will be reviewed for their seriousness, and patients with major deviations will be excluded from the PP population.

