3.5 Missing Data Handling and Derivation Rules

For safety data analysis, no imputation will be performed on the missing data and analysis will be based on observed cases.

For efficacy endpoints, the continuous variables will be summarized and analyzed as recorded on the case report forms (CRFs). If statistically significant imbalances are detected in the incidence of changes in DBS settings and outcome impacting medication use as well as the frequency of PRN drug or rescue medication between the initial study and the extension study, a Mixed-Effect Model Repeated Measure (MMRM) model will be used as the analysis method to compare the change in score from baseline between the initial study and the extension study for patients who received placebo in initial study (TIRCON2012V1) and the analysis will be based on observed cases. If no significant imbalance was detected, the paired t-test will be used as the analysis method and the last observed data will be used.

For the efficacy analysis on all patients who received DFP during the initial and the extension study, the last observation will be used to calculate the change from baseline for patients terminated early. As a sensitivity analysis, for early termination due to worsening of disease conditions or inadequate efficacy of the drug, as indicated in the CRF, the “worst score” method will be used for data imputation. That is, for continuous variables such as BAD total score at a particular time point, the worst score of all patients will be used to impute the missing data at that time point. For categorical variable such as responder, the worst category (treatment failure) will be assigned. For missing data due to missed visit, the last observation will be used to fill the void.

For BAD total score, if one or several component scores cannot be measured, then the same component score from the last visit will be carried forward and if it is also missing, the score from the next visit will be carried backward to fill the missing component score(s) before the total score is calculated.

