Date of exposure will be defined as day 1 for all duration calculations. For example, age at entry will be calculated as the integer value of the expression: (date of exposure – date of birth) / 365.25. For patients on DFP in the initial study, the date of exposure during the initial study (TIRCON2012V1) will be used while for those switched from placebo to DFP in the extension study (TIRCON2012V1-EXT), the date of exposure during the extension study will be used.

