3.6 Statistical Software and Level of Significance

All statistical analyses will be performed using SAS (version 9.3 or higher) on Windows operating system. Null hypotheses tested are that there are no differences in true parameter between comparison groups, unless otherwise stated. A two-sided *p*-value of 0.05 will be used as the significance level for the determination of statistical significance in all statistical tests.

4 Statistical Analyses

The efficacy endpoints are defined as follows:

All patients:

- Change in the BAD total score from baseline (defined as prior to the start of deferiprone therapy) to Visit 4, as assessed by central evaluation of videotapes
- Proportion of patients with improved or unchanged BAD scale total score between baseline and Visit 4 (responder analysis, responders defined as change in BAD total score to be ≤ 0)
- Change from baseline to Visit 4 in BAD scale score per body region (eyes, mouth, neck, trunk, and each upper and lower extremity), as assessed by central evaluation of videotapes
- PGI-I score at Visit 4
- Proportion of patients showing an improvement on PGI-I at Visit 4 (responder analysis, responders are defined as patients whose conditions have not deteriorated; patients who have “no change”, or are “minimally improved”, “much improved” or “very much improved” in the PGI-I questionnaire at the last study visit)

The time points for these efficacy endpoints are defined as follows:

- For patients who received deferiprone in the initial study, the baseline visit of that study will be treated as the baseline visit of TIRCON2012V1-EXT as well. Thus, Visit 1 of the extension study (Week 0) will be Year 1.5 (month 18), and Visit 4 (Week 78) will be Year 3 (month 36).
- For patients who received placebo in the initial study, Visit 1 of the extension study (Week 0) will be the baseline visit. Thus, Visit 4 (Week 78) will be Year 1.5 (month 18).

Patients who received placebo in initial study:

For this group only, for each measure, the changes seen between the start and completion of the initial study (TIRCON2012V1) (i.e., following 18 months on placebo) will be compared against the changes seen between the start and completion of extension study (TIRCON2012V1-EXT) (i.e., following 18 months on deferiprone), as follows:

- Comparison of change in BAD total score from baseline to completion of the initial study vs. change in BAD total score from baseline to completion of the extension study

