extension study. Continuous variables will be compared by paired t-tests while proportions by McNemar's test. If statistically significant imbalances are detected, they will be adjusted accordingly for the comparison of changes in BAD and PGI-I between the initial study and the extension study by using a MMRM model approach that is consistent with the analysis of these two efficacy measures in the initial study. The MMRM model is specified below.

The MMRM model will be applied to non-imputed data from the observed cases (OC) data set. Let y_i denote the vector of n_i continuous post-baseline measurements observed for study patient i . Each response (i.e., each element of y_i) will be defined as the patient's score at that occasion minus the baseline score.

The model will assume that the distribution of y_i is multivariate normal,

$$y_i \sim N(X_i\beta, \Sigma_i),$$

where X_i is a design matrix of dimensions $n_i \times p$, β is a vector of coefficients of length p , and Σ_i is an $n_i \times n_i$ covariance matrix.

The MMRM model will include baseline value of the outcome as a covariate and treatment group as the main factor in the model. A change in DBS settings or use of medications that have the potential to affect dystonia symptoms during the study may confound the treatment effect assessment (named outcome impacting medication use hereafter) for DFP vs. placebo between the initial study and the extension study for patients who were on placebo in the initial study. Hence, both variables will also be included in the MMRM model as visit-dependent covariates.

The visit-dependent covariate for DBS settings change is defined as follows: for patients with DBS at enrollment, if there is any DBS setting change since the previous visit, it will be coded as 'DBS Setting Change' for the current visit or 'No DBS Setting Change' otherwise. For example, if a patient has a DBS setting change between the outcome assessment dates at month 6 visit and month 12 visit, it will be coded as 'DBS Setting Change' for month 12 visit in the model. For those patients without DBS at enrollment, it will be coded as 'No DBS'. A discrete variable, DBSCHG, with three categories will be included in the MMRM model.

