The visit-dependent covariate for the outcome impacting medication use will be defined according to whether the patient is on a regular dosing regimen or on a PRN (as needed) dosing regimen between two visits. For patients treated on a regular dosing regimen, if there is a dose change or starting of new medication since the previous visit, it will be coded as 'Yes' for the current visit and the future follow-up visits or 'No' otherwise in the model. For patients who do not use any outcome impacting medication, it will be coded as 'No'.

For patients on a PRN (as needed) dosing regimen, the visit-dependent covariate will be defined according to the treatment impact period in the following table.

Medication	Treatment impact period
Baclofen	30 days
Trihexyphenidyl	30 days
Clonazepam	30 days
Tizanidine	30 days
Botox	60 days
Tetrabenazine	90 days

If the PRN drug is started within the treatment impact period prior to the assessment date of an outcome for a visit, it will be coded as ‘Yes’ for that visit. If the drug is started outside this time window but is not interrupted within this period, it will also be coded as ‘Yes’ for that visit. Under other conditions, it will be coded as ‘No’ in the model. A binary variable for the outcome impacting medication use, RESMED, will be included in the MMRM model.

The frequency of PRN drug or rescue medication use between two outcome assessment dates of current visit and the previous visit will also be included in the MMRM model as a quantitative visit-dependent covariate, NDRUG, for the current visit.

The MIXED procedure in SAS will be used for the MMRM model analysis. Data within each patient at different visits will be considered repeated measures. AR(1) (autoregressive of order 1) covariance structure will be used to model the correlation between repeated measures within the same patient and Kenward and Roger’s method will be used to estimate the denominator degrees of freedom. The 95% confidence interval (CI) for the difference between the two treatments will be calculated by the LSMEANS statement.

A sample SAS code for the MMRM model is presented in the box below:

```
proc mixed;
  class TREAT USUBJID VISIT DBSCHG RESMED;
  model CHG=TREAT VISIT TREAT*VISIT BASE DBSCHG RESMED
  NDRUG/solution ddfm=kr;
  repeated VISIT/ subject=USUBJID type=ar(1);
  lsmeans TREAT*VISIT / diff cl;
run;
```

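### If an imbalance triggers the MMRM for former-placebo patients, its sample code cannot be fitted: each patient has two records at the same VISIT level, so the covariance is singular

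*SAP*

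**What the plan says.** SAP section 3.5 makes the MMRM conditional. If a significant imbalance is found in DBS changes, outcome-impacting medication, or PRN and rescue use, the model is used "to compare the change in score from baseline between the initial study and the extension study for patients who received placebo in initial study"; otherwise a paired t-test is used. Section 4 repeats the rule for setting the two studies against each other: "If statistically significant imbalances are detected, they will be adjusted accordingly for the comparison of changes in BAD and PGI-I between the initial study".

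The sample code in SAP section 4 has TREAT, VISIT, their interaction, baseline and three visit-dependent covariates as fixed effects. Its REPEATED line reads "repeated VISIT/ subject=USUBJID type=ar(1" (closing bracket omitted here). There is no RANDOM statement and no term for study period. USUBJID is defined as the patient ID, and VISIT as the scheduled visit after baseline.

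Four other provisions determine what the data set looks like:

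- Protocol 5.4, on patient numbers: "These assigned numbers will be maintained for patients who continue on to study TIRCON2012V1-EXT".
- SAP 3.5, on the clock: "for those switched from placebo to DFP in the extension study (TIRCON2012V1-EXT), the date of exposure during the extension study will be used".
- SAP section 4, on baseline: "For patients who received placebo in the initial study, Visit 1 of the extension study (Week 0) will be the baseline visit". Extension Visit 4 is therefore month 18 for these patients.
- The shells for Tables 14.2.2.1 to 14.2.2.7 use Month 6, 12 and 18 both for placebo in the initial study and for deferiprone in the extension.

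**The concern.** An AR(1) structure indexed by VISIT within patient suits a parallel-group trial, where each patient contributes one record per visit. Here every patient contributes two periods under one ID, with the same visit labels. The code treats the two Month 6 records, one on placebo and one on deferiprone, as the same occasion and so as perfectly correlated. A Gaussian likelihood needs the inverse and the log-determinant of each patient's covariance block, and a singular block has neither.

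The MMRM is called on exactly when the unadjusted comparison is thought to be confounded. If the specified model cannot be fitted at that point, someone must pick another covariance structure, probably with the data in view. The possible repairs give different standard errors. Protocol 9.4.1.3 left the modelling approach to be detailed in the SAP, so this is where it should be settled.

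**Working it through.** The documents give no sample-size or power figure to reproduce. The check is on the algebra of the specified covariance. SAS was not run.

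**Inputs.** Former-placebo patients: 24 (SAP 3.2: "44 originally randomized to the deferiprone group and 24 in the placebo group"). VISIT levels: Month 6, 12 and 18, coded 1, 2, 3, in each period. Maximum records: 24 × 6 = 144. The autocorrelation ρ is not in the documents, so a range is used.

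**Step 1: the block as written.** Element (j, k) of one patient's correlation matrix is ρ^|v_j − v_k|. Two records at the same level have |v_j − v_k| = 0, so their correlation is ρ⁰ = 1 for any ρ.

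| VISIT levels present | Size | Rank | Determinant (ρ = 0, 0.3, 0.6, 0.9) |
|---|---|---|---|
| 1,2,3,1,2,3 (complete) | 6 | 3 | 0 at each |
| 1,2,3,1,2 | 5 | 3 | 0 at each |
| 1,2,3,1 (one extension visit) | 4 | 3 | 0 at each |

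**Step 2: how many patients are affected.** Enrolment requires completion of the initial study, and the ITT definition requires patients to "have a baseline and at least one post-baseline efficacy assessment in the extension study". Nearly every patient therefore shares at least one visit level across periods, and one shared level makes the block singular.

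**Step 3: can other SAP rules rescue it?** The rule in section 4 that averages multiple measurements at one visit would merge placebo and deferiprone values. Study-specific IDs would let the code run, but they contradict the definition of USUBJID and Protocol 5.4, and they discard the pairing.

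**Step 4: which repair?** Assume linear progression for each patient, with SD s over 18 months, and independent visit error with SD e. Neither SD is in the documents. The placebo Month 18 score is also the extension baseline, so the covariances between placebo and deferiprone changes in BAD are:

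- Month 6: s²/9
- Month 12: 4s²/9
- Month 18: s² − e²

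With e = 1.5 these are 0.11, 0.44, −1.25 at s = 1; 0.44, 1.78, 1.75 at s = 2; and 1.00, 4.00, 6.75 at s = 3. The sign can differ by visit.

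The Month 18 difference has variance 6e², because the slope cancels. Its true SE with 24 patients is √(6 × 2.25 / 24) = 0.75 at every s. Large-sample model-based SEs are:

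| Structure | Parameters | s = 1 | s = 2 | s = 3 | Error over e = 1 to 2 |
|---|---|---|---|---|---|
| Unstructured, six levels | 21 | 0.75 | 0.75 | 0.75 | none |
| un@ar(1), period by visit | 4 | 0.66 | 0.69 | 0.72 | −13% to +2% |
| AR(1), six levels | 2 | 0.63 | 0.70 | 0.79 | −17% to +25% |

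**Step 5: is the unstructured fit feasible?** Simulated REML fits with 24 patients, at s = 1 and 3, with and without baseline, converged in 2,000 of 2,000 data sets. With complete data the mean SE was 0.73 to 0.75 against an empirical SD of 0.71 to 0.74. With 20% of patients losing late extension visits it was 0.75 to 0.77 against 0.79 to 0.84. These fits omitted DBSCHG, RESMED and NDRUG and applied no Kenward-Roger correction.

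**The case against.** The strongest reply is that VISIT could be coded on a 36-month axis with six levels. The section 4 visit windows run from Month 6 to Month 36, and the shell for Table 14.2.1.1 prints Month 24 to 36 rows under the Placebo-DFP column. With that coding AR(1) has full rank (determinant 0.62 at ρ = 0.3 and 0.11 at ρ = 0.6). Half the TREAT-by-VISIT cells are empty, but that is not fatal: the LSMEANS statement requests all pairwise cell differences, and deferiprone Month 36 minus placebo Month 18 is estimable.

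This is correct as far as it goes, and it limits the finding to the coding that the SAP's own definitions imply. Those definitions do not support the alternative. Both baseline and date of exposure restart at extension entry for these patients, the former-placebo shells use Month 6, 12 and 18 twice, and the Month 24 to 36 rows sit on a grid shared with patients on deferiprone throughout.

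Other points carry some weight. The code is labelled a sample, and a singular block fails visibly instead of biasing an estimate. But the surrounding prose also names AR(1) over visits and says nothing about two records at one visit. The SAP asks for consistency with the initial study's analysis, whose plan is not available here. A period-by-visit MMRM keeps that approach, although the covariance changes from AR(1). Up to 21 covariance parameters from about 24 patients is a real burden, and the simulations did not include the confounding covariates.

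**Conclusion.** The concern holds. Under the SAP's definitions of patient, visit and baseline, the triggered MMRM has no likelihood: the block has rank 3 of 6 with complete data and determinant 0 at every ρ tested. This conclusion rests on algebra and needs no assumed SD. Only the comparison of repairs depends on the assumed progression and error SDs.

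The consequence is bounded. It arises only if the imbalance trigger is met, it concerns a secondary comparison in at most 24 patients (144 records), and it leaves the paired t-test and McNemar analyses untouched. The separate trend model for deferiprone time points has one record per visit per patient and is not affected. The point should be fixed before analysis, because Table 14.2.2.9 has no other adjusted counterpart and the choice of repair changes the standard error.

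**What to change.** Keep VISIT as Month 6, 12 and 18 in the MODEL and LSMEANS statements, so that the deferiprone-minus-placebo difference at each visit stays directly available. Derive a six-level period-by-visit factor, for example PERVIS, add it to CLASS, and replace the REPEATED line with `repeated PERVIS / subject=USUBJID type=un;`, keeping Kenward-Roger degrees of freedom.

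Pre-specify `repeated TREAT VISIT / subject=USUBJID type=un@ar(1);` as the fallback if the unstructured fit does not converge. State that the fallback does not capture the shared Month 18 and baseline value: in the assumed process with e = 1.5 its SE is 4% to 13% too small.

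Do not use `subject=USUBJID*TREAT`, which drops the pairing, or plain AR(1) on six levels. The shared-value argument applies to BAD change scores but not to PGI-I, which is analysed directly.

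The cost is one derived variable, one changed line of code with its fallback, and one sentence in the SAP. No new data are needed. The statistical price is up to 21 covariance parameters in place of 2, which is why the fallback (4 parameters) should be written down now.

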- Comparison of the proportion of patients with improved or unchanged BAD scale total score between baseline and completion of the initial study vs. the proportion

with improved or unchanged BAD scale total score from baseline to completion of the extension study (responder analysis)

- Comparison of the change in BAD score per body region between baseline and completion of the initial study vs. change in BAD score per body region between baseline and completion of the extension study
- Comparison of PGI-I score at the completion of the initial study vs. PGI-I score at the completion of the extension study
- Comparison of the proportion of patients showing an improvement on PGI-I at completion of the initial study vs. the proportion showing an improvement at completion of the extension study (responder analysis)

The following time window will be employed to classify the efficacy data into each scheduled visit according to the time elapsed from the first medication date (date of exposure) to the assessment date:

Month 6 visit: 3 to <9 months

Month 12 visit: 9 to <15 months

Month 18 visit: 15 to <21 months

Month 24 visit: 21 to <27 months

Month 30 visit: 27 to <33 months

Month 36 visit: 33 to <39 months

The exact calculation of time elapsed from the date of exposure to the sample assessment date is: $\text{Time elapsed} = (\text{date of sample assessment}) - (\text{date of exposure}) + 1$. The resulting time elapsed will be expressed in months and will be used for data tabulation and trend analysis. If multiple measurements for an outcome are available at the same visit for a subject, the average value will be used for that outcome for this subject at that visit.

A paired t-test will be used to assess the statistical significance of the changes in the efficacy outcomes from baseline to the end of study. For the BAD total score and for PGI-I, the proportions of patients determined to be responders at the end of study will be calculated and presented along with 95% confidence intervals.

The incidence of changes in DBS settings and outcome impacting medication use as well as the frequency of PRN drug or rescue medication use will be tabulated by visit and treatment group for patients on placebo in the initial study. The incidence of changes in DBS settings and outcome impacting medication use as well as the frequency of PRN drug or rescue medication use will be compared between the initial study and the

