where TREAT is the indicator variable for treatment group (DFP vs. Placebo), USUBJID represents the patient ID, VISIT is the discrete variable representing the scheduled study visit after the baseline visit, DBSCHG is the discrete variable with three categories for

DBS settings change (DBS Setting Change, No DBS Setting Change, No DBS), RESMED is the binary variable for outcome impacting medication use (Yes vs. No), CHG is the change in value of efficacy outcome from baseline to the scheduled visit, BASE is the baseline value of efficacy outcome, and NDRUG is the frequency of PRN drug or rescue medication use.

PGI-I is already a measurement of change from baseline and thus will be used directly as the outcome variable and baseline BAD score will be included as the baseline value in all models.

McNemar's test will be used to compare the proportion of responders in the initial study with the proportion of responders in the extension study.

For all patients who were on DFP in both studies, the longitudinal response profile for BAD score will be explored by a MMRM model with time modelled as a continuous variable.

For this model, AR(1) (autoregressive of order 1) covariance structure will be used to model the correlation between repeated measures within the same patient and Kenward and Roger's method will be used to estimate the denominator degrees of freedom.

A sample SAS code for this MMRM model is presented in the box below:

```
proc mixed;  
  class USUBJID VISIT;  
  model BAD= TIME /solution ddfm=kr;  
  repeated VISIT/ subject=USUBJID type=ar(1);  
run;
```

where USUBJID represents the patient ID, VISIT is the discrete variable representing the scheduled study visit after the baseline visit, BAD is the value of BAD score at each time point, and TIME is the time in months at each time point corresponding to each visit.

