4.3.1 Efficacy Endpoints

All patients:

For the efficacy measures of BAD (total score and by body region) and PGI-I, the value at each of the measurement time points defined in section 4 will be determined and summarized using descriptive statistics for all patients on DFP treatment. Similar data will also be presented by the treatment group received in initial study.

A paired t-test will be used to assess the statistical significance of the changes in these efficacy outcomes from baseline to the end of study (Visit 4, month 18 or 36 as defined in section 4).

For the BAD total score and for PGI-I, the proportions of patients determined to be responders at the end of study (Visit 4) will be calculated and presented along with 95% confidence intervals.

The mean trajectory of BAD (total score and by body region) and PGI-I by time will be plotted. The longitudinal trend for BAD total score and by body region will be explored by the MMRM model with time modelled as a continuous variable as defined in section 4 for all time points where patients were on DFP.

Patients who received placebo in initial study:

For the efficacy measures of BAD (total score and by body region) and PGI-I, the value at each of the measurement time points defined in section 4 will be determined and summarized using descriptive statistics for each study period.

A paired t-test will be used to compare the change in BAD (total score and by body region) between the start and completion of the initial study to that between the start and completion of the extension study. The same test will be repeated for the PGI-I data.

The incidence of changes in DBS settings and outcome impacting medication use as well as the frequency of PRN drug or rescue medication use will be tabulated and compared between the initial study and the extension study. If statistically significant imbalances are detected, they will be adjusted accordingly for the comparison of changes in BAD and PGI-I between the initial study and the extension study by using the MMRM model as defined in section 4.

For the BAD total score and for PGI-I, McNemar's test will be used to compare the proportion of responders in the initial study with the proportion of responders in the extension study.

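### As written, the exploratory BAD trend model starts at Month 6 and leaves out the pre-deferiprone score, although that score is a valid time-zero value of its outcome

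*SAP*

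**What the plan says.** SAP section 4 gives code for a trend model with time as a continuous variable. Its mean model is "model BAD= TIME /solution ddfm=kr": an intercept and a linear term in months, with the raw BAD score as outcome and no baseline term. The covariance is AR(1) over visits within patient. The legend states that "VISIT is the discrete variable representing the scheduled study visit after the baseline visit".

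SAP 4.3.1 applies the model to BAD total and each body region "for all time points where patients were on DFP". SAP section 4 defines the change endpoint as running from "baseline (defined as prior to the start of deferiprone therapy) to Visit 4", so the baseline visit is not an on-deferiprone time point. The list of efficacy windows opens with "Month 6 visit: 3 to <9 months" and has no month-0 entry.

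The SAP is not consistent on who enters. The sentence before the trend code names patients on deferiprone in both studies. SAP 4.3.1 places the model under all patients, and the title of Table 14.2.1.17 says all patients.

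**The concern.** In the SAP's other repeated-measures model the outcome is change from baseline and the baseline score is a covariate. Baseline cannot be a response there, so restricting VISIT to later visits is right. The trend model is different. Its outcome is the raw score, so the baseline score is an ordinary observation at time zero. Under the legend it enters neither as outcome nor as covariate.

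Two things follow. The slope describes the course from Month 6 on and carries nothing about what happens between starting deferiprone and Month 6. It is also estimated from fewer points than were collected: six visits instead of seven for patients on deferiprone throughout, and three instead of four for those who switched from placebo. Table 14.2.1.17 will attach a confidence interval and p-value to this slope for the total score and every region, in support of a secondary objective about change in dystonia over time.

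**Working it through.** **What enters the model.** Three statements point the same way: the VISIT legend, the on-deferiprone restriction in SAP 4.3.1, and the window list. The code has no baseline covariate. The SAP's instruction to use baseline BAD as the baseline value concerns models for PGI-I and has no counterpart in this code.

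**Inputs for the precision check**
- Group sizes (SAP 3.2): 44 on deferiprone in both studies, 24 switched from placebo, 68 in total.
- Visits (SAP section 4): Months 6, 12, 18, 24, 30, 36 for the 44, and Months 6, 12, 18 for the 24.
- Covariance: AR(1), as in the SAP code.
- Correlation between visits 6 months apart, rho: **assumed** 0.5 to 0.95.

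The plan states no slope, standard error or power for this model, so there is no figure of its own to reproduce.

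**Formula.** Var(slope) is the slope element of the inverse of the sum over patients of X'R⁻¹X. X holds an intercept and time in months, and R has entries rho^|j−k| for visits j and k. The residual SD cancels in the ratio of standard errors.

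**Hand check at rho = 0, 44 patients.** Var(slope) is then proportional to 1/Σ(t − mean t)². Months 6 to 36 have mean 21 and sum of squares 2 × (15² + 9² + 3²) = 630. Months 0 to 36 have mean 18 and sum of squares 2 × (18² + 12² + 6²) = 1008. The ratio of standard errors is √(1008/630) = √1.6 = 1.265, an excess of 26.5%, which agrees with the matrix calculation.

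**Results** (residual SD = 1)

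| rho | SE without month 0, n=68 | SE with month 0, n=68 | Excess, n=68 | Excess, n=44 |
|---|---|---|---|---|
| 0.5 | 0.00622 | 0.00513 | 21.2% | 20.4% |
| 0.7 | 0.00585 | 0.00496 | 18.0% | 16.8% |
| 0.8 | 0.00527 | 0.00454 | 16.2% | 14.6% |
| 0.9 | 0.00412 | 0.00361 | 14.1% | 12.2% |
| 0.95 | 0.00306 | 0.00271 | 13.1% | 10.9% |

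Over rho from 0 to 0.99 the excess runs from 26.7% down to 12.2% (n=68) and from 26.5% down to 9.8% (n=44). With 10 to 30% attrition and all 68 patients it stays between 13.4% and 21.9% for rho 0.5 to 0.95.

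**What the slope describes if the course is not linear.** Illustrative mean course: BAD falls 2 points by Month 6, then stays flat (68 patients).
- Month 6 onward only: slope 0 at every rho.
- One line including month 0: slope −0.052 (rho 0.5) to −0.066 (rho 0.95) points per month, although nothing changes after Month 6.
- One line plus a separate term for the first 6 months: post-Month 6 slope 0. Its standard error equals that of the model without month 0 (0.00585 at rho 0.7).

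So the precision gain belongs to the single line through month 0, and only if that line is right.

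**The case against.** The strongest reply is that this is loose wording in an exploratory analysis. The VISIT phrase repeats the legend of the change-score model, where it is correct. The on-deferiprone phrase has another obvious purpose, which is to keep the switchers' placebo-period scores out. The shells titled for all patients on deferiprone (Tables 14.2.1.2 and 14.2.1.4) carry a Baseline row. That stands as far as intent goes: the documents do not show a deliberate decision to drop baseline. But those tables report summaries and change by visit, and nothing says that a month-0 record goes into the trend model. A programmer following the legend would leave it out.

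Three stronger inferences are tempting and are not supported.
- **That the plan throws away the pre-deferiprone score, or would hide an early change.** It does so in this model only. Tables 14.2.1.3 and 14.2.1.4 test change from baseline at Month 6 and each later visit, Table 14.2.1.15 tests change to Visit 4, and the BAD responder analyses use baseline. An early change followed by a plateau would give a flat slope in Table 14.2.1.17 but would show in those tables.
- **That the 13 to 21% is a known loss.** It depends on an assumed correlation, on all 68 patients entering, and on linearity from month 0. No sample size or power rests on this slope.
- **That adding month 0 is enough.** The step-then-plateau example shows that a single line through month 0 would misreport it as a steady decline.

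**Conclusion.** The concern holds for the SAP as written: the slope in Table 14.2.1.17 describes Month 6 onward, and a valid time-zero observation is left out of a raw-score model without a stated reason. If the course is linear and the 6-month AR(1) correlation is 0.5 to 0.95, the standard error is about 13 to 21% larger than it need be with 68 patients, or 11 to 20% with 44. The direction is the same at every correlation tried. If the course is not linear, the issue is which period the slope describes, and the precision comparison does not apply. Because the analysis is exploratory and change from baseline is tested elsewhere, the priority is low to moderate.

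**What to change.** - In the trend-model legend in SAP section 4, define VISIT and TIME to include the pre-deferiprone visit as month 0. That is the initial-study baseline for patients on deferiprone throughout and extension Visit 1 for those who switched. Apply this to the total score and each region.
- Amend SAP 4.3.1 so that the data run from the pre-deferiprone baseline through every later visit on deferiprone.
- State one population for the model, so that SAP section 4, SAP 4.3.1 and the title of Table 14.2.1.17 agree.
- Add a linearity check, such as a separate term for months 0 to 6, and report the post-Month 6 slope as a sensitivity analysis whatever the check shows.

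The cost is a few sentences, one extra record per patient and extra rows in one table. No new data are needed, since the baseline scores are already tabulated. The downside is that a single line through month 0 can misdescribe an early step; the last item is there to expose that.
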